8. Have received any investigational product for the treatment of GA within the past 6 months or 5 half-lives (whichever is longer), other than nutritional supplements such as the age-related eye disease study (AREDS) formula
9. Have received a gene or cell therapy at any time
10. Have a contraindication to the specified protocol corticosteroid regimen
11. Are unwilling to use two forms of contraception (one of which being a barrier method) for 90 days post-dosing, if relevant
12. Active malignancy within the past 12 months, except for: Appropriately treated carcinoma in situ of the cervix, non-melanoma skin carcinoma, or prostate cancer with a stable prostate-specific antigen (PSA) ≥ 12 months
13. Have any other significant ocular or non-ocular medical or psychiatric condition which, in the opinion of the Investigator, may either put the subject at risk or may influence the results of the study
14. Cohorts 5 to 7 only: presence of metallic objects or implanted stimulator devices in or near the head, including cochlear implants, deep brain stimulators, vagus nerve stimulators, and other implanted electrodes or stimulators

DOSE/ROUTE/REGIMEN:

The study drug is supplied to the surgical site as a vial of frozen sterile liquid.

GT005 is an aqueous suspension of recombinant AAV2 vector particles in [REDACTED]

[REDACTED] GT005 is administered at ambient temperature as a single subretinal injection into the macula of the study eye.

Surgical procedure

GT005 will be administered subretinally via the transvitreal procedure for Cohorts 1 to 4, an approach which is based on publicly available methodology. GT005 will be administered subretinally via a suprachoroidal cannulation with the Orbit SDS for Cohorts 5 to 7 (US sites only). All Cohorts will be treated by an appropriately qualified vitreoretinal surgeon in an operating room under local anaesthesia. Other anaesthetic options will be considered by the surgeon as appropriate for the subject. The total duration of the surgery is about 1 hour. The detailed procedure is described in the relevant Surgical Manuals.

In brief:

Cohorts 1 to 4

[REDACTED]

Cohorts 5 to 7 (US sites only)

[REDACTED]

DURATION OF TREATMENT AND FOLLOW-UP

Subjects will receive a single subretinal injection and will be followed for up to 240 weeks (5 years) post-dosing.

REFERENCE TREATMENT:

Only one eye will be treated in the study and the untreated fellow eye will be the comparator.

The eye with the worse visual acuity will be the study eye. If visual acuity is equivalent in both eyes, the eye with the largest area of GA will be the study eye unless the patient (in consultation with the surgeon) expresses an alternative preference. The study eye will be confirmed by the vitreoretinal surgeon.

STATISTICAL METHODS: All the efficacy data (anatomical and functional visual outcomes), [REDACTED] and [REDACTED] data and safety data (including laboratory safety) collected will be amalgamated into a single database with datasets constructed according to these categories. Unless otherwise stated, data will be summarised in aggregate by dose and route of administration. Further detail will be described in the statistical analysis plan.

Analysis Set

Two analysis sets will be defined. The Safety Analysis Set (SAF) will include all subjects who have undergone surgery and received GT005. The SAF will be used for analysis of safety and laboratory data. The Full Analysis Set (FAS) will include all subjects in the SAF who have baseline and at least one post-baseline value of GA area size via FAF in the study eye. The FAS will be used for analysis of efficacy data.

Data Descriptions

Data will be summarised by the subject population (SS, FAS, and subsets as applicable), Cohort/dose group (Cohorts 1 to 7, dose group [REDACTED] vg, and overall subjects), eye (Treated [Study Eye]/Untreated [Fellow Eye] for ocular evaluations and tests), and assessment (Weeks 1 to 48, or early termination, where appropriate). The long-term follow-up data (Visits 9 to 13) will be reported separately.

Categorical variables will be summarised as the number and percentage of subjects, and frequencies of events (if appropriate). Continuous variables will be summarised as number of subjects, mean, median, standard deviation, minimum, and maximum statistics. Graphical displays appropriate to these types of data may be used to present any important findings.

Demographics and Baseline Characteristics

Medical history and measures at baseline including: demographics, medical/surgical history, concomitant medication, laboratory safety, urine pregnancy testing will be summarised descriptively by dose and route of administration. No formal comparisons of the Cohorts will be made. Assessments made at screening/baseline

and post-surgery will only be included in their respective safety and efficacy tables, together with any post-baseline assessments.

Efficacy Assessments

Efficacy assessments to evaluate the anatomical and functional visual outcomes involve: GA area size (via FAF), [REDACTED]

[REDACTED], [REDACTED], [REDACTED] For continuous variables, the change from baseline will be derived and presented together with actual values over time (visit) by dose and route of administration, and by eye (Treated [Study Eye]/Untreated [Fellow Eye]). Categorical variables from any ocular evaluations will be presented by classification over time (visit) by dose and route of administration, and by eye (Treated [Study Eye]/Untreated [Fellow Eye]).

[REDACTED]
[REDACTED]
[REDACTED]
[REDACTED]

Safety Assessments

Safety evaluations are considered to be of key importance for this study and include: AEs, ophthalmic examinations, BCVA (ETDRS) score, vital signs, laboratory safety (biochemistry and haematology), and [REDACTED]

Adverse events will be summarised in two parts: systemic events and ocular events. For systemic events, data will be summarised by dose and route of administration. Ocular events will be summarised by dose and route of administration and by eye (Treated [Study Eye]/Untreated [Fellow Eye]).

All AEs (Overall, by seriousness, by severity, by relationship to GT005 or the procedure) recorded throughout the investigation will be reported following classification according to the Medical Dictionary for Regulatory Activities dictionary (for system organ class and preferred term).

Systemic safety evaluations including vital signs, laboratory safety [REDACTED] will be summarised over time by dose and route of administration.

Ocular safety evaluations including ophthalmic examination variables (cataract grading, intra-ocular pressure, etc.) and BCVA scores, will be summarised in the same manner as ocular efficacy variables, dependent on data type.

Power and Sample Size

As this is a first in human exploratory Phase I/II study, no formal sample size has been calculated.

MONITORING COMMITTEES

Data Safety Monitoring Board (DSMB)

Composition

A DSMB will be formed to review all safety data at predetermined intervals during the study. Additional DSMB meetings may be held as needed or at the request of the DSMB members. The DSMB is an independent committee that includes at least three individuals who cumulatively have the clinical and medical expertise to monitor the safety of subjects in the clinical study and will include a minimum of

one clinician expert in the management of AMD and clinical immunology. The DSMB will be chaired by one of the clinical experts who will attend all meetings. No DSMB member will be an Investigator in this study.

Roles and Responsibilities of DSMB

The roles and responsibilities of the DSMB are defined in the DSMB Charter, which include, but are not limited to:

- Monitoring and reviewing all safety issues relative to the conduct of the study
- Ensuring the protection and safety of subjects participating in the study
- Recommending dose escalation in accordance with available safety data and study stopping rules
- Recommending a different BCVA threshold for entry into the study, as appropriate
- Providing recommendations to continue, modify the design, suspend or terminate the study depending upon emerging safety data
- Communicating other recommendations or concerns as appropriate

[figure not shown]
Dose Escalation

- The DSMB will meet after the third subject has been enrolled (recruitment and treatment will continue at the current dose – there will be no study hold) in Cohorts 1 to 3, and in Cohort 5
- If treatment has been tolerated and stopping rules have not been met, the DSMB will recommend to Gyroscope that enrolment of the next study Cohort can commence
- Screening of potential subjects will be allowed prior to the DSMB meeting and decision, but treatment must not be administered to subjects in the higher dose group until the outcome of the DSMB recommendation has been provided in writing to Gyroscope

Details regarding the DSMB mission and content of the DSMB data safety reviews will be specified in the DSMB charter.

STUDY DESIGN

Figure 1: Overview of the Study Design (Part 3 and 4 are US only)

Abbreviations: DSMB=data safety monitoring board; n=number of subjects; SDS=subretinal delivery system; vg=vector genomes.

SCHEDULE OF ASSESSMENTS

Table 1: Clinical Schedule (Screening to Week 48)

	Local Site ¹	Surgical Site					Surgical or Local Site			Local Trial Site ¹			Early Termination Visit	
Assessment	Visit 1 Screening ² Day -56 to -1 (-8 weeks)	Visit 2 Dosing			Tel call	Visit 3 ⁴ Week 1 ±3 days	Tel call Week 2 ±3 days	Visit 4 Week 5 -7/+3 days	Visit 4.1 Week 8 ±7 days	Visit 5 Week 12 ±7 days	Visit 6 Week 24 ±7 days	Visit 7 Week 36 ±7 days	Visit 8 Week 48 ±7 days	
		Pre-surgery Day 1 ³	Surgery Day 1	Post-surgery Day 2		Week 1 ±3 days	Week 2 ±3 days	Week 5 -7/+3 days	Week 8 ±7 days	Week 12 ±7 days	Week 24 ±7 days	Week 36 ±7 days	Week 48 ±7 days	
Informed consent	X													X ⁵
Review of Inc/Exc criteria	X													
Demographics	X													
Medical/surgical history	X	X												
Concomitant medication	X	X		X		X		X	X	X	X	X	X	
Urine pregnancy test ⁶	X	X ⁷												
Vital signs	X	X		X		X		X	X	X	X	X	X	
Biochemistry/Haematology	X				X		X		X	X	X	X	X	
Serum sample for CFI levels ⁸	X													
Sample for sequencing of complement genes ⁸	X													
Surgery and dosing (GT005)			X											
Discharge from unit				X										
Adverse events – AE/TEAE/TESAE ¹⁵	X	X	X	X	X	X	X	X	X	X	X	X	X	

	Local Site ¹	Surgical Site				Surgical or Local Site			Local Trial Site ¹			Early Termination Visit
Assessment	Visit 1 Screening ²	Visit 2 Dosing		Tel call	Visit 3 ⁴	Tel call	Visit 4	Visit 4.1	Visit 5	Visit 6	Visit 7	Visit 8
	Day -56 to -1 (-8 weeks)	Pre-surgery Day 1 ³	Surgery Day 1		Post-surgery Day 2	Week 1 ±3 days	Week 2 ±3 days	Week 5 -7/+3 days	Week 8 ±7 days	Week 12 ±7 days	Week 24 ±7 days	Week 36 ±7 days

Abbreviations: AAV2=adeno-associated virus vector serotype 2; AE=adverse event; BCVA=best corrected visual acuity; CFI=complement factor I; FAF=fundus autofluorescence; ICF=informed consent form; Inc/Exc=inclusion/exclusion; LLVA=low luminance visual acuity; TEAE=treatment-emergent adverse events; Tel=telephone; TESAE=Treatment-emergent serious adverse events.

1. Dependent upon location and Sponsor approvals, a Surgical Site may also act as a Local Site.
2. Screening assessments may be conducted over several days. The 8-week screening period may be extended up to 12 weeks if agreed by the Sponsor Medical Monitor. If the screening period is extended past the original 8 week screening period (8–12 weeks), standard ophthalmic exam, haematology/biochemistry, and visual acuity (BCVA/LLVA) assessments should be repeated. In the event the GT005 administration is deferred during the surgical procedure (e.g., due to an AE occurring during surgery) the screening period may be extended up to 16 weeks if agreed by the Sponsor Medical Monitor. Additionally, if the screening period is extended past 12 weeks (12–16 weeks), in case of GT005 deferral, standard ophthalmic exam, haematology/biochemistry, visual acuity (BCVA/LLVA), and FAFs will be repeated.
3. Pre-surgery assessments will include any local requirements of the surgical site. Pre-surgery assessments should be performed within 7 days prior to surgery.
4. Visit 3 will take place at the assigned surgical site, however this may be held at the local site if more practical.
5. Subjects will be consented using a separate ICF for the additional four years of long-term follow-up at this visit.
6. Only for women of childbearing potential.
7. Urine pregnancy test (for women of childbearing potential) if the one performed at screening is more than 14 days old.
8. Not required at Screening if already available through participation in a previous Gyroscope sponsored study.

14. 12 to 24 hours post dosing, prior to discharge.
 15. All AEs should be captured from signing the informed consent form. Additional imaging or functional assessments may be conducted, as needed, to allow for safety assessment.

Table 2: Schedule of Visual Tests (Screening to Week 48)

Assessment	Local Site ¹	Surgical Site					Surgical or Local Site			Local Trial Site ¹			Early Termination Visit
	Visit 1 Screening ²	Visit 2 Dosing		Tel call	Visit 3 ⁴ Week 1 ±3 days	Tel Call Week 2 ±3 days	Visit 4 Week 5 -7/+3 days	Visit 4.1 Week 8 ±7 days	Visit 5 Week 12 ±7 days	Visit 6 Weeks 24 ±7 days	Visit 7 Week 36 ±7 days	Visit 8 Week 48 ±7 days	
	Day -56 to -1 (-8 weeks)	Pre-surgery Day 1 ³	Surgery Day 1	Post-surgery Day 2									
Standard ophthalmic examination	X			X		X		X	X	X	X	X	X
Pre-surgery ocular safety check		X ⁵											
Colour fundus photography	X								X	X	X	X	X
Fundus autofluorescence	X						X		X	X	X	X	X
OCT macula	X			X	X		X		X	X	X	X	X
OCT-A ⁷	X									X ⁸			X ⁸
Fluorescein angiography ⁷	X									X ⁸			X ⁸
Microperimetry ⁹	X	X ¹⁰							X	X		X	X
Additional functional assessments (if required) ¹¹													X ¹¹
Visual Acuity: BCVA and LLVA using ETDRS	X				X ¹²		X ¹²	X ¹²	X	X	X	X	X
Visual acuity check		X ¹³											

Submission of historical FAFs and/or OCTs ¹⁵	X

Abbreviations: BCVA=best corrected visual acuity; CNV=choroidal neovascularisation; ETDRS=early treatment diabetic retinopathy study chart; FA=fluorescein angiography; LLVA=low luminance visual acuity; MAIA=macular integrity assessment; MNRead=Minnesota low vision reading; OCT=optical coherence tomography; OCT-A=optical coherence tomography angiography; Tel=telephone; [REDACTED].
 
1. Dependent upon location and Sponsor approvals, a Surgical Site may also act as a Local Site2. Screening assessments may be conducted over several days. The screening period may be extended up to a maximum of 12 weeks, if agreed by the Sponsor Medical Monitor. If the screening period is extended past the original 8-week screening period (8–12 weeks), standard ophthalmic exam, haematology/biochemistry, and visual acuity (BCVA/LLVA) assessments should be repeated. In the event the GT005 administration is deferred during the surgical procedure (e.g., due to an AE occurring during surgery) the screening period may be extended up to 16 weeks if agreed by the Sponsor Medical Monitor. Additionally, if the screening period is extended past 12 weeks (12–16 weeks), in case of GT005 deferral, standard ophthalmic exam, haematology/biochemistry, visual acuity (BCVA/LLVA), and FAFs will be repeated.3. Pre-surgery assessments should be performed within 7 days prior to surgery.4. Visit 3 will take place at the surgical site, however this may be held at the local site if more practical.5. A pre-surgery ocular safety check will be performed to verify no new adverse events that could halt surgery. [REDACTED]7. Other imaging modalities may be performed to assess for CNV if OCT-A is not available. In the event that the OCT/OCT-A images are inconclusive to rule out the presence of CNV the subject will be required to undergo an additional assessment via FA. At the Investigator's discretion, FA may also be performed initially prior to the OCT/OCT-A results being available, but this is not mandatory.8. OCT-A and/or fluorescein angiography may be performed during the study period if clinically indicated, for example, if a subject converts to wet AMD.9. Microperimetry should be performed during scheduled visits at sites with a MAIA microperimeter: Microperimetry will be performed at either screening or prior to surgery (within the screening visit window) and may be performed over >1 day if needed. If in the view of the Investigator, the subject is not capable of performing the test, this will not be considered an exclusion to study participation. Microperimetry assessment instructions will be provided in the imaging manual.10. If omitted at screening, assessments should be performed during the pre-surgery visit. [REDACTED]12. LLVA is not performed at Visits 3, 4 and 4.1.13. A visual acuity check using ETDRS or Snellen chart (near card is permissible) must be performed on the study eye if >4 weeks have lapsed since the last BCVA with ETDRS assessment. If Snellen result is >3 lines (BCVA equivalent to 15 letters) worse than the previous BCVA ETDRS score, then a BCVA with ETDRS assessment must be repeated. If the BCVA ETDRS score in the study eye is either >15 letters worse than the previous BCVA ETDRS score or <24 letters score (Cohorts 4 to 7), the surgery must be postponed pending discussion and approval by the Sponsor Medical Monitor. [REDACTED]15. Enrolled subjects will be asked if they are willing to consent to have historical FAF and/or OCT images that were obtained within 1 year prior to enrolment, if available, provided to the sponsor.	

[REDACTED]
	

[REDACTED]
	

[REDACTED]
	

Table 3: Follow-up Schedule (Week 72 to Week 240)

Assessment	Local Trial Site ¹					Unscheduled Visit/ Early Termination ²
	Visit 9 Week 72 (Year 1.5) ±30 days	Visit 10 Week 96 (Year 2) ±30 days	Visit 11 Week 144 (Year 3) ±30 days	Visit 12 Week 192 (Year 4) ±30 days	Visit 13 Week 240 (Year 5) ±30 days	
Standard ophthalmic examination	X	X	X	X	X	X
Colour fundus photography	X	X	X	X	X	X
Fundus autofluorescence	X	X	X	X	X	X
OCT macula	X	X	X	X	X	X
OCT-A ³			X ⁴			X ⁴
Fluorescein angiography ³			X ⁴			X ⁴
Visual acuity: BCVA/LLVA using ETDRS	X	X	X	X	X	X
Microperimetry	X	X	X	X	X	X
Additional functional assessments (if required) ⁶	X	X	X	X	X	X
AE/SAE monitoring ⁷	X	X	X	X	X	X
Concomitant medication	X	X	X	X	X	X
Submission of historical FAFs and/or OCTs ⁹				X		
Abbreviations: AAV2=adeno-associated virus vector serotype 2; AE=adverse event; BCVA=best corrected visual acuity; CFI=complement factor I; CNV=choroidal neovascularisation; ETDRS=early treatment diabetic retinopathy study chart; FA=fluorescein angiography; LLVA=low luminance visual acuity; MNRead=Minnesota low vision reading; OCT=optical coherence tomography; OCT-A=optical coherence tomography angiography; SAE=serious adverse event; [REDACTED] [REDACTED].						
1. Dependent upon location and Sponsor approvals, a Surgical Site may also act as a Local Site						
2. Minimum study assessments shown; additional assessments may be performed if clinically indicated. [REDACTED]						
3. Other imaging modalities may be performed to assess for CNV if OCT-A is not available. In the event that the OCT/OCT-A images are inconclusive to rule out the presence of CNV the subject will be required to undergo an additional assessment via FA. At the Investigator's discretion, FA may also be performed initially prior to the OCT/OCT-A results being available, but this is not mandatory.						
4. OCT-A and/or fluorescein angiography may be performed during the study period if clinically indicated, for example, if a subject converts to wet AMD.						

Assessment	Local Trial Site ¹					Unscheduled Visit/ Early Termination ²
	Visit 9 Week 72 (Year 1.5) ±30 days	Visit 10 Week 96 (Year 2) ±30 days	Visit 11 Week 144 (Year 3) ±30 days	Visit 12 Week 192 (Year 4) ±30 days	Visit 13 Week 240 (Year 5) ±30 days	
7.	Additional tests/assessments (i.e., blood tests, imaging or functional assessments) may be conducted, as needed, to allow for safety monitoring.					

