	
Consolidation and expansion of the objectives and evaluation criteria.
 
Reduced the number of primary objective evaluation criteria.
 
Update to the evaluation criteria for the secondary objective to evaluate the effect of GT005 on anatomical and functional visual outcomes.
 
Update to secondary objectives for the Orbit SDS cohort in the US only.
 
[REDACTED]
 
[REDACTED]
 
[REDACTED]
 
[REDACTED]
 
[REDACTED]
 
[REDACTED]
 
[REDACTED]
 
[REDACTED]
	
To include the objectives and evaluation criteria from both the US- and UK-specific protocols, and to further define the objectives and evaluation criteria.
 
Updated to report the main primary objective/evaluation criteria assessed and clarified that the endpoint will be evaluated over 48 weeks.
 
Moved criteria on BCVA from the primary evaluation criteria to be reported as a secondary objective in the study. Added that the endpoints will be evaluated over 48 weeks.
 
Updated to include the specific endpoint and not the performance target. [REDACTED]
 
[REDACTED]
 
[REDACTED]
 
[REDACTED]
 
[REDACTED]
 
[REDACTED]
 
[REDACTED]
 
[REDACTED]

	Inclusion/Exclusion Criteria.	
To broaden and provide further clarity on the study eligibility criteria:
 
Inclusion criterion 2 has been revised to include a broader population of patients with GA (unilateral or bilateral), with a requirement of AMD in the contralateral eye (except if the subject is monocular), but no requirement of GA in the fellow eye.
 
Inclusion criterion 3 has been revised to allow GA lesion total size in the study eye $\geq 1.25\text{mm}^2$ with no upper limit in Cohort 7 only.

Protocol Version	Change	Justification
		
Inclusion criterion 3 and criterion 4 have been revised to remove the requirement related to the GA lesion in the fellow eye in Cohorts 4 to 7.
 
Inclusion criterion 5 has been revised to remove the BCVA requirement for the fellow eye in Cohorts 4 to 7.
 
Exclusion criterion 1 has been revised to allow inclusion of subjects with CNV in the fellow eye (given specific criteria).
 
Exclusion criteria 2, 3, 5, 6, and 7 have been revised to apply criteria to the study eye only, to broaden inclusion of subjects into the study.

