1.9. Population

Subjects with bilateral GA due to AMD in the absence of neovascularisation will be enrolled into the study.

As this is a FIH study, subjects with GA due to AMD and already some vision loss in the study eye have been chosen for Part 1 (Cohorts 1 to 3; dose-escalation). On completion of the dose escalation and review of the safety data by the Data Safety Monitoring Board (DSMB), subjects with better preserved vision, who potentially would be more likely to benefit from treatment, will be entered into Parts 2 (Cohort 4), 3 (Cohorts 5 to 6), and 4 (Cohort 7) of the study.

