4.2. Inclusion Criteria

For inclusion in the study, subjects must fulfil all of the following criteria:

1. Able and willing to give consent to study participation
2. Have a clinical diagnosis of GA secondary to AMD in the study eye, as determined by the Investigator, and a diagnosis of AMD in the contralateral eye (except if the subject is monocular)
3. Cohorts 1 to 6: GA lesion(s) total size in the study eye must be $\geq 1.25\text{mm}^2$ and $\leq 17.5\text{mm}^2$
Cohort 7: GA lesion(s) total size in the study eye must be $\geq 1.25\text{mm}^2$
4. GA lesion(s) in the study eye must reside completely within the FAF fundus image
5. Cohorts 1 to 3: BCVA of ≤ 50 letters (6/36 Snellen acuity equivalent or worse) using ETDRS charts in the study eye
Cohorts 4 to 7: BCVA of ≥ 24 letters (6/95 and 20/320 Snellen acuity equivalent or better) using ETDRS charts in the study eye
6. Aged ≥ 55 years
7. Able to attend all study visits and complete the study procedures
8. Women of child-bearing potential need to have a negative urine pregnancy test within two weeks prior to receiving the drug. A pregnancy test is not required for postmenopausal women (defined as being at least 12 consecutive months without menses) or those surgically sterilised (those having a bilateral tubal ligation/bilateral salpingectomy, bilateral tubal occlusive procedure, hysterectomy, or bilateral oophorectomy)

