4.3. Exclusion Criteria

Subjects must not enter the study if any of the following exclusion criteria are fulfilled:

1. Have evidence or history of CNV in the study eye. Subjects are permitted to have CNV in the fellow eye defined as either:
 - a. Non-exudative/sub-clinical fellow eye CNV identified at screening, or

- b. Known history of fellow eye CNV with either ≥ 2 years since diagnosis or with no active treatment required in 6 months prior to screening
- 2. Presence of moderate/severe non-proliferative, diabetic retinopathy or worse in the study eye
- 3. Have history of vitrectomy, sub-macular surgery, or macular photocoagulation in the study eye
- 4. History of intraocular surgery in the study eye within 12 weeks prior to Screening (Visit 1). [REDACTED]
- 5. Have clinically significant cataract that may require surgery during the study period in the study eye
- 6. Presence of moderate to severe glaucomatous optic neuropathy in the study eye; uncontrolled IOP despite the use of more than two topical agents; a history of glaucoma-filtering or valve surgery is also excluded
- 7. Axial myopia of greater than -8 diopters in the study eye
- 8. Have received any investigational product for the treatment of GA within the past 6 months or 5 half-lives (whichever is longer), other than nutritional supplements such as the age-related eye disease study (AREDS) formula
- 9. Have received a gene or cell therapy at any time
- 10. Have a contraindication to the specified protocol corticosteroid regimen
- 11. Are unwilling to use two forms of contraception (one of which being a barrier method) for 90 days post-dosing, if relevant
- 12. Active malignancy within the past 12 months, except for: Appropriately treated carcinoma in situ of the cervix, non-melanoma skin carcinoma, or prostate cancer with a stable prostate-specific antigen (PSA) ≥ 12 months
- 13. Have any other significant ocular or non-ocular medical or psychiatric condition which, in the opinion of the Investigator, may either put the subject at risk or may influence the results of the study
- 14. Cohorts 5 to 7 only: presence of metallic objects or implanted stimulator devices in or near the head, including cochlear implants, deep brain stimulators, vagus nerve stimulators, and other implanted electrodes or stimulators

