6.6. Blinding and Randomisation

This is an open label study. All participants will receive GT005.

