11.3.2. Efficacy

Efficacy assessments to evaluate the anatomical and functional visual outcomes involve: GA area size (via FAF), [REDACTED]
[REDACTED], macular mean sensitivity via Microperimetry, [REDACTED]

For continuous efficacy variables the change from baseline will be derived and presented together with actual values over time (visit) by dose and route of administration and by eye (Treated [Study Eye]/Untreated [Fellow Eye]). Categorical variables from any ocular evaluations will be presented by classification over time (visit) by dose and route of administration and by eye (Treated [Study Eye]/Untreated [Fellow Eye]).

The GA area size data will be compared to historical data on natural disease progression, including pre-treatment data from FOCUS subjects if available.

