11.3.4.1. Ophthalmic Examination

Ophthalmic examinations will be displayed as continuous (actual and change from baseline values), or categorical data as appropriate by dose and route of administration, and by eye (Treated [Study Eye]/Untreated [Fellow Eye]) for each assessment. For continuous data evaluations, differences and change from baseline differences between Treated and Untreated eyes will also be presented by dose and route of administration for each assessment.

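### The fellow eye is named as comparator, but the criteria require only AMD in it and permit CNV, so the by-eye acuity and efficacy displays mix fellow eyes at different AMD stages and sub-types

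*Protocol*

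**What the plan says.** Under Reference Treatment, the synopsis says: "Only one eye will be treated in the study and the untreated fellow eye will be the comparator". There is no control arm (Protocol 6.6: "This is an open label study. All participants will receive GT005"). For GA area, Protocol 11.3.2 names a second reference: "The GA area size data will be compared to historical data on natural disease progression, including pre-treatment data from FOCUS subjects if available".

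Inclusion criterion 2 (Protocol 4.2) asks, beyond GA in the study eye, for "a diagnosis of AMD in the contralateral eye (except if the subject is monocular". Exclusion criterion 1 (Protocol 4.3) bars CNV in the study eye only: "Subjects are permitted to have CNV in the fellow eye defined as either" sub-clinical disease found at screening or a known history meeting a time or treatment condition. Protocol 1.9 describes a different population: "Subjects with bilateral GA due to AMD in the absence of neovascularisation will be enrolled into the study".

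Protocol 11.3.2 presents efficacy variables by treated and untreated eye. For continuous ophthalmic data, Protocol 11.3.4.1 goes further: "differences and change from baseline differences between Treated and Untreated eyes will also be presented by dose and route of administration". Protocol 11.3.4.2 applies the same presentation to BCVA and LLVA, which Section 2 lists as secondary endpoints. SAP 3.1 presents ocular evaluations by eye where appropriate. SAP 3.9.2 presents BCVA, LLVA and low-luminance deficit by eye, as actual values and change from baseline.

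**The concern.** A fellow eye can stand in for the untreated course of the study eye only if both eyes would follow a similar course without treatment. An eye with AMD but no GA has no lesion to enlarge and may keep its acuity for reasons unrelated to GT005. The acuity of an eye with CNV may follow exudation and its treatment. When such eyes are averaged with true GA fellow eyes, the treated-minus-untreated difference reflects baseline diagnosis as well as treatment.

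The secondary objective on anatomical and functional outcomes is at stake, chiefly the between-eye differences in BCVA and LLVA. A reader could not tell a drug or surgical effect from a difference in fellow-eye disease. Comparisons between doses or routes could also shift merely because the fellow-eye mix differs.

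**Working it through.** **1. What eligibility guarantees for each eye (Protocol 4.2 and 4.3).**

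| Attribute | Study eye | Fellow eye |
|---|---|---|
| Diagnosis | GA secondary to AMD | AMD of any stage; waived if monocular |
| GA size | at least 1.25 mm² (Cohorts 1–6: also at most 17.5 mm²) | no condition |
| GA within FAF image | required | no condition |
| BCVA | at most 50 letters (Cohorts 1–3) or at least 24 (Cohorts 4–7) | no condition |
| CNV | excluded | allowed if sub-clinical, or known for 2 years or more, or untreated for 6 months |

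The last two CNV conditions are joined by either/or. Read literally, an eye diagnosed two or more years ago qualifies while still under treatment. None of this fits Protocol 1.9.

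**2. Whether any rule sorts fellow eyes before analysis.** The FAS depends on study-eye FAF only (SAP 2.1). Baseline ocular characteristics are summarised for the study eye only (SAP 3.5). Ocular history is listed for both eyes without a summary table (SAP 3.6). Censoring covers alternative GA treatment in the study eye only (SAP 2.2). No visible text limits which fellow eyes enter a by-eye display, or shows in a table how many have GA, CNV or neither.

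**3. Effect on the acuity difference.** Let T be the mean change in treated eyes, taken as the same whatever the fellow eye's status. Let fellow eyes comprise shares p(G), p(E) and p(C) with GA and no CNV, AMD without GA, and CNV, with mean changes m(G), m(E) and m(C). The shares sum to 1.

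- Contrast against all fellow eyes: T − [p(G)m(G) + p(E)m(E) + p(C)m(C)]
- Contrast against GA fellow eyes: T − m(G)
- First minus second: p(E)[m(G) − m(E)] + p(C)[m(G) − m(C)]

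If GA eyes lose more letters than eyes without GA, the first term is negative and counts against GT005. The second can take either sign. The documents give none of these quantities, so neither the size nor the direction of the sum can be stated.

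**4. Illustration for a by-eye GA display (Protocol 11.3.2 only).** Assume that a share u of fellow eyes has no GA and is recorded as zero growth, and that GA eyes grow by g. The fellow-eye mean is then (1 − u)g. With no treatment effect, the treated/untreated growth ratio a reader would form is 1/(1 − u):

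- u = 10%: 1/0.90 = 1.11
- u = 25%: 1/0.75 = 1.33
- u = 50%: 1/0.50 = 2.00

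With true relative slowing r, the apparent slowing is 1 − (1 − r)/(1 − u). At an assumed r = 20%:

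- u = 10%: 1 − 0.80/0.90 = 11%
- u = 20%: 1 − 0.80/0.80 = 0%
- u = 30%: 1 − 0.80/0.70 = −14%

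Every u and r here is assumed. If eyes without GA are left missing rather than scored zero, this bias does not arise and the two columns rest on different subjects instead.

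**5. Why the mix probably differs by cohort.** The V8.0 entry (16 February 2022) records the broadened diagnosis, "but no requirement of GA in the fellow eye", the removal of the fellow-eye lesion and BCVA conditions in Cohorts 4 to 7, and the admission of fellow-eye CNV. A log entry placed before V6.1 (17 November 2020) already refers to Part 1 dose escalation as complete. Summaries by dose and route therefore combine or contrast subjects enrolled under different fellow-eye rules.

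**The case against.** The strongest reply is that the planned GA analysis does not use the fellow eye. SAP 3.7 summarises and models GA area and its square root in the study eye, with no eye term. That stands. A reader might infer from the ratios above that the trial's GA result is biased by 11% to 100%. The documents do not support this: neither specifies a between-eye GA ratio or difference, and the shares are assumed.

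A reader might also infer that the anatomical objective has no other reference. Protocol 11.3.2 names historical and pre-treatment growth, which does not depend on fellow-eye status. It is not concurrent, however, and it covers GA area only, not acuity.

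Between-eye differences are specified only in Protocol 11.3.4.1 and 11.3.4.2, under Safety; SAP 3.9.2 shows values and changes by eye without a difference. That narrows the point but does not remove it: SAP Section 4 declares no change from the protocol's analyses, and side-by-side columns invite the same comparison.

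The displays are descriptive, no testing is planned (SAP 3.1), and the primary objective is TEAE incidence. Many transvitreal subjects may also predate V8.0: SAP version 1 (6 February 2023) preceded an interim with data up to Week 72 from Cohorts 1–4. These points limit the consequence, but the number of unmatched fellow eyes remains unknown.

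Two further readings go too far. Monocular subjects do not contaminate the comparison; they supply no usable fellow-eye data and drop out. Nor are the fellow eyes best described as having different diseases: Protocol 1.1 treats GA and neovascular AMD as two forms of late AMD.

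Finally, text beside the by-eye efficacy statements is blacked out, so the absence of a restriction can be asserted only for the visible text.

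**Conclusion.** The point holds for the by-eye displays. The comparator named in the synopsis is not secured by the current criteria, and Protocol 1.9 contradicts inclusion criterion 2 and exclusion criterion 1. The planned BCVA/LLVA differences, and the by-eye efficacy and acuity displays, mix fellow eyes at different AMD stages and sub-types, probably to a different degree by cohort.

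The size is unknown. For acuity the direction is also unknown. For a by-eye GA display the bias would run against GT005 if eyes without GA are scored as zero growth. The study-eye GA models and the primary safety endpoint are not affected. This should be corrected before the by-eye results are reported, but it does not undermine the study's main conclusions on safety.

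**What to change.** **Efficacy and acuity displays (Protocol 11.3.2 and 11.3.4.2; SAP 3.1, 3.7 and 3.9.2).** For BCVA, LLVA, microperimetry and any by-eye GA display, present the treated-versus-untreated contrast in subjects whose fellow eye at baseline has centrally measured GA and no evidence or history of CNV. Show the remaining fellow eyes separately in two groups: AMD without GA, and CNV.

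**Baseline table (SAP 3.5).** Add fellow-eye status by dose and route: GA without CNV, AMD without GA, CNV, monocular.

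**Safety.** Keep fellow-eye adverse events and safety examinations (IOP, cataract grading, ophthalmic examination) complete for all subjects. Limiting these by GA status would split small cohorts and lose safety information.

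**Later CNV.** Do not drop fellow-eye values after CNV develops in the main display; a rule for one eye only would be a one-sided post-baseline selection. At most, add a sensitivity display that treats conversion the same way in both eyes.

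**Wording.** Align the synopsis comparator sentence with this, and reconcile Protocol 1.9 with inclusion criterion 2 and exclusion criterion 1.

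**Cost.** The data are already planned: FAF in both eyes with central quantification and OCT of each eye (Protocol 8.2.3), and ocular history (Protocol 8.1.2). The change needs wording and one table. The price is fewer subjects in the matched contrast. That contrast remains descriptive and still reflects the default choice of the worse-seeing eye as study eye, which grouping by fellow-eye status does not remove.
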